Hypothesis and Specific Aims	
Hypothesis#1: A 12-month treatment with combination ACTHar gel and Tacrolimus therapy will be superior to ACTHar gel therapy alone in lowering urinary protein to creatinine (UP/Cr) ratios in patients with idiopathic DNA-JB9 positive Fibrillary GN
 
Specific Aim #1-will randomize 35 patients with biopsy proven DNA-JB9 positive Fibrillary glomerulopathy to receive a 12-month course of ACTHar gel at 80 units SQ 2X/week alone or in combination with oral Tacrolimus at 1.0 mg BID (targeting for trough Tacrolimus dose of 4-6 ng/ml).
 
Hypothesis#2: Treatment with combination ACTHar gel and Tacrolimus therapy will result in a higher eGFR after 24 months of follow up than patients randomized to ACTHar gel therapy alone
 
Specific Aim #2-will determine the change in eGFR from baseline to 24 months of follow for patients with biopsy proven DNA-JB9 positive Fibrillary glomerulopathy. It is anticipated that at 24 months (12 months after completing therapy) patients randomized to ACTHar gel plus Tacrolimus will have higher eGFR compared to patients receiving ACTHar gel alone.
 
Hypothesis #3: Combination therapy of ACTHar Gel and Tacrolimus in patients with DNA-JB9 positive Fibrillary Glomerulopathy will lead to significantly lower urinary markers of podocyte injury compared to patients receiving ACTHar gel therapy alone.
 
Specific Aim #3-will compare the relative changes in the following urinary biomarkers will be performed:
 
1. Urinary VEGF 121, VEGF-1652. Urinary VEGF-189, VEGF-2063. Urinary MCP-14. Urinary Synaptopodin5. Urinary TGF-beta6. Urinary Podocalyxin7. Urinary Nephryn 
Levels will be measured at baseline prior to treatment and after 12 months of ACTHar ge therapyl alone or in combination with oral Tacrolimus. The relative reduction urinary biomarkers will also be compared between the two treatment groups.

Study Population	
A total of 34 patients will be enrolled.
 
Group 1 (17 patients) ACTHar gel 80 units 2X/week alone for 12 months of therapy.
 
Group 2 (17 patients) ACTHar gel 80 units 2X/week plus oral Tacrolimus 1.0 mg BID titrated to trough Tacrolimus levels between 4-6 ng/ml
 
Anticipated drop out rate 10%.

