Secondary Endpoint	Secondary Endpoints: 
1) The relative change in UP/Cr at 24 months (12 months after stopping both ACTH and Tacrolimus) in the ACTHar gel group and the ACTHar gel + Tacrolimus group.2) The percentage of patients in the ACTHar gel alone versus ACTHar gel + Tacrolimus group that achieves complete, partial or clinical responses after 12 months of therapy3) The change in eGFR (measured by CKD-EPI formula) between the ACTHar gel and ACTHar Gel + Tacrolimus groups after 24 months of treatment with ACTHar gel alone or in combination with oral Tacrolimus. In addition, we will also compare the relative change in eGFR between those patients receiving ACTHar gel alone with those randomized to combination therapy.4) To compare the change in urinary biomarkers (see below) at baseline and after 12 months of treatment with ACTHar gel alone or in combination with Tacrolimus. The patients urinary biomarker levels after 12 months of therapy will be compared between the ACTHar gel alone group and ACTHar gel + Tacrolimus group.
a) Urinary VEGF 121, 165 189, and206b) Urinary MCP-1c) Urinary Synaptopodind) Urinary TGF-betae) Urinary Podocalyxinf) Urinary Nephryn 
Fibrillary GN patients with concurrent Type II diabetes mellitus: To determine whether ACTHar gel therapy resulted in

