The sample size was calculated to detect a 40% difference in the mean UP/Cr ratio after 12 -month of ACTHar gel therapy alone or with oral Tacrolimus. Analysis will be intention to treat for all patient receiving at least one week of drug therapy. Based on the estimated variability of 30% for the change in UP/Cr ratio (CV) a sample size of 17 patients per arm (total-34) will be needed to provide 80% power to see a difference with a P value of < 0.05. A Fisher exact test will be applied for comparisons of adverse event frequencies. All tests were two-tailed with a P value-0.05 considered significant.

References:

- 1) Laser Microdissection and Proteomic Analysis of Amyloidosis, Cryoglobulinemic GN, Fibrillary GN, and Immunotactoid Glomerulopathy Sanjeev Sethi,* Jason D. Theis,* Julie A. Vrana,* Fernando C. Fervenza,† Anjali Sethi,‡ Qi Qian,† Patrick Quint,* Nelson Leung,* Ahmet Dogan,* and Samih H. Nasr* *Clin J Am Soc Nephrol* 8: 915–921, 2013.
- 2) Fibrillary Glomerulonephritis: A Report of 66 Cases from a Single Institution *Samih H. Nasr,* Anthony M. Valeri,† Lynn D. Cornell,* Mary E. Fidler,* Sanjeev Sethi,* Nelson Leung,‡ and Fernando C. Fervenza‡ Clin J Am Soc Nephrol* 6: 775–784, 2011.
- 3) Fibrillary Glomerulonephritis and Immunotactoid Glomerulopathy Charles E. Alpers and Jolanta Kowalewska. *J Am Soc Nephrol* 19: 34–37, 2008.
- 4) Plasmapheresis leading to remission of refractory

14March2019

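### One unadjusted 0.05 rule covers all tests, so the secondary superiority hypotheses (24-month eGFR, urinary markers) can be called significant even when the 12-month UP/Cr primary fails

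*Protocol*

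**What the plan says.** All of this is in the protocol synopsis and the visit schedule.

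- **Primary Endpoint** names one endpoint, the change in UP/Cr after 12 months of treatment. The statistical paragraph sizes the trial on it alone: "The sample size was calculated to detect a 40% difference in the mean UP/Cr ratio", with 17 patients per arm "needed to provide 80% power to see a difference with a P value of < 0.05".
- **Hypothesis and Specific Aims** states three superiority hypotheses for the combination arm. The first is 12-month UP/Cr. The second begins "Treatment with combination ACTHar gel and Tacrolimus therapy will result in a higher eGFR after 24 months of follow up than" and names the ACTHar-alone arm as comparator. The third says the combination "will lead to significantly lower urinary markers of podocyte injury compared to patients receiving ACTHar gel therapy alone". Each has its own specific aim.
- **Secondary Endpoint** lists four items. Item 1 is "The relative change in UP/Cr at 24 months (12 months after stopping both ACTH and Tacrolimus"; item 2 is the percentage of patients in each arm "that achieves complete, partial or clinical responses after 12 months of therapy"; item 3 is eGFR at 24 months; item 4 is the urinary markers.
- **Statistical Analysis Sample Size and Power** closes with "All tests were two-tailed with a P value-0.05 considered significant". It gives no adjustment, no testing order and no statement that secondary results are supportive.
- **The visit schedule** places urinary VEGF, MCP-1, TGF-beta and synaptopodin under a heading that calls them exploratory.

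**The concern.** The protocol is not merely silent on multiplicity. It fixes a significance rule for every test and separately words two of its secondary endpoints as superiority hypotheses, one of them in terms of a significant difference. Suppose the 12-month UP/Cr comparison gives p = 0.30 and the 24-month eGFR comparison gives p = 0.04. Under the written rule the second result is significant and Hypothesis #2 is met, although the endpoint the trial was designed around showed nothing.

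In a 34-patient trial sized for one endpoint, such an isolated result is a realistic false lead. It could also carry weight, because the Background says the disease has no approved or generally accepted therapy. The markers add to the difficulty: they are a formal hypothesis, a secondary endpoint and exploratory, depending on where one looks.

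**Working it through.** **The plan's own figure.** The only stated error rate is 0.05 two-sided per test; there is no familywise figure to reproduce. The one stated calculation is the sample size. Its inputs (difference 40%, "Based on the estimated variability of 30% for the change in UP/Cr ratio (CV"), taken as a mean difference of 40 with SD 30, give n = 2 × (1.96 + 0.84)² × (30/40)² = 8.8, so 9 per arm (10 with the t distribution), not 17. That mismatch is a separate matter and does not affect what follows.

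**Inputs.**
- Level per test: 0.05 two-sided, or 0.025 in each direction (statistical paragraph).
- Three tests: Hypotheses #1 to #3, each reduced to one test. Four tests: these plus 24-month UP/Cr (secondary item 1).
- Assumed, not in the protocol: all null hypotheses true; normal test statistics, signed so that positive favours tacrolimus; equal correlation r, shown at 0, 0.5 and 0.8.

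**Formulas.** With r = 0:
- either direction: 1 − 0.95³ = 14.3%; 1 − 0.95⁴ = 18.5%
- favouring tacrolimus: 1 − 0.975³ = 7.3%; 1 − 0.975⁴ = 9.6%

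With r > 0, write each statistic as √r·U + √(1−r)·Eᵢ, with U and Eᵢ independent standard normals. Given U = u, the statistics are independent. The chance of no rejection in k tests is therefore the average over u of [Φ((1.96 − √r·u)/√(1−r)) − Φ((−1.96 − √r·u)/√(1−r))]^k. For errors favouring tacrolimus only, drop the second Φ term. These integrals were evaluated numerically.

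| Chance of at least one false positive | r = 0 | r = 0.5 | r = 0.8 |
|---|---|---|---|
| 3 tests, either direction | 14.3% | 12.5% | 9.8% |
| 4 tests, either direction | 18.5% | 15.6% | 11.4% |
| 3 tests, favouring tacrolimus | 7.3% | 6.3% | 4.9% |
| 4 tests, favouring tacrolimus | 9.6% | 7.8% | 5.7% |

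The references for a single test are 5% and 2.5%. At r = 0.5 the ratio is 2.5 for three tests (12.5/5 and 6.3/2.5) and 3.1 for four (15.6/5 and 7.8/2.5).

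**Primary fails, something else is significant.** The primary alone is significant 5% of the time under the null, so this chance is the either-direction figure minus 5%. At r = 0.5 it is 12.5 − 5 = 7.5% for three tests and 15.6 − 5 = 10.6% for four.

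**What is left out.** One response test would make five tests: about 18% in either direction and 9% favouring tacrolimus at r = 0.5. Hypothesis #3 covers nine analytes (four VEGF isoforms and five others) with no composite. Testing each separately gives 13 tests: about 33% and 17% at r = 0.5. The table is therefore the mild case.

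**After the fix.** If a secondary is tested only after a significant primary, then with all nulls true a false claim requires the primary to be rejected, so the rate is 5% in either direction. A fixed sequence keeps it at or below 5% whichever nulls are true.

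**The case against.** The strongest reply is that the protocol does rank its endpoints. It names one primary, lists eGFR and the markers as secondary, labels the month-12 and month-24 visits as primary and secondary evaluations, and sizes on the primary alone. This stands: it would be wrong to infer that the tests have no order or that the primary's error rate is inflated. What the tiers lack is a consequence, because the same significance rule applies to every tier.

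Second, a multiplicity procedure for secondary endpoints is commonly left to the statistical analysis plan, which is not at hand. This also stands, and the absence of such a procedure is not the point here. The point is that the protocol states an unadjusted rule for all tests, which an analysis plan with gating would have to depart from.

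Third, the sentence can be read as giving only sidedness and a nominal level, since it follows the Fisher test for adverse events. That is fair as far as it goes: the protocol nowhere says that a significant secondary confirms a hypothesis. But the sentence covers all tests and uses the word significant, and Hypothesis #3 is worded in the same terms.

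Fourth, a reader might take 12% to 16% as the chance of a false claim for tacrolimus. It is not: those figures count errors in both directions, and roughly half of them would favour ACTHar gel alone.

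**Conclusion.** The concern holds in a limited form. The primary comparison keeps its 0.05 and the sample size is unaffected. The defect is that a blanket unadjusted 0.05 sits beside superiority wording for 24-month eGFR and the urinary markers, with nothing tying those claims to the primary.

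At an assumed correlation of 0.5, with all nulls true and one test per hypothesis, the chance of a false claim for tacrolimus is 6.3% (three tests) or 7.8% (four), two and a half to three times the 2.5% of a single test. The absolute size depends on the correlation and on how many markers and response categories are tested. That a secondary can be claimed after a failed primary does not depend on either. It is worth correcting before the data are analysed, but it does not threaten the primary result.

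**What to change.** In the statistical paragraph:

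1. Limit the two-sided 0.05 claim of significance to the primary comparison, the between-arm difference in UP/Cr at month 12.
2. Allow a claim of significance for a secondary endpoint only in a fixed sequence stated in advance, starting after a significant primary and stopping at the first non-significant result. Hypothesis #2 could come next, but the order is the sponsor's choice; the Secondary Endpoint list puts 24-month UP/Cr first.
3. Report all other secondary endpoints and the markers as supportive, with estimates and 95% confidence intervals. If the sponsor wants no secondary claims, one sentence labelling all of them supportive is enough.

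Then reword Hypothesis #3 so that it no longer promises a significant difference, and give the markers one status across the hypotheses, the secondary endpoint list and the visit schedule.

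The cost is wording: no added patients, visits or data, and the primary keeps its full 0.05. The downside is that a secondary result cannot be claimed as significant if the primary fails.

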Trough Levels (if in Tacrolimus Group)						X	X			
Exploratory Laboratory Assessments										
Urinary		X	X	X		X	X		X	X
VEGF										
Urinary		X	X	X		X	X		X	X
MCP-1										
Urinary		X	X	X		X	X		X	X
TGF-beta										
Urinary		X	X	X		X	X		X	X
Synapto										
Urinary		X	X	X		X	X		X	X
Future Proteins										
**1: National PI & Local PI to review patient records for study eligibility prior to Pre-Randomization Visit 1										
**2: HgbA1c will be optional for diabetic patients left to discretion of the site PI										
**3: 14 Days Post Randomization (Visit 4) will be optional for patients traveling from long distances. Would request that patient visit nephrologist in home town if any adverse events of concern are reported.										
**4: 14 Days Post End of Treatment (Visit 9) will be optional for patients traveling from long distances. Would request that patient visit nephrologist in home town if any adverse events of concern are reported.

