3. LIST OF ABBREVIATIONS

AE	adverse event
AESI	adverse event of special interest
ALT	alanine transaminase
AST	aspartate transaminase
AUC	area under the concentration-time curve
BUN	blood urea nitrogen
β-hCG	beta-human chorionic gonadotropin
CBC	complete blood count
CFR	Code of Federal Regulations
CHD	coronary heart disease
CKD	chronic kidney disease
CMP	comprehensive metabolic panel
CRA	clinical research associate
CRO	contract research organization
CVA	cerebrovascular accident
DNA	deoxyribonucleic acid
eCRF	electronic Case Report Form
ECG	Electrocardiogram
EDC	electronic data capture
EOS	End-of-Study (visit)
EOT	End-of-Treatment (visit)
ESRD	end-stage renal disease

FDA	Food and Drug Administration
FSI	first subject in
GCP	Good Clinical Practice
GLP	Good Laboratory Practice
HIPAA	Health Insurance Portability and Accountability Act
HIV	human immunodeficiency virus
ICF	informed consent form
ICH	International Conference on Harmonisation
ID	Identification
IEC	Independent Ethics Committee
IND	Investigational New Drug application
INR	International Normalized Ratio
IOM	Institute of Medicine
LSLV	last subject last visit
MedDRA	Medical Dictionary for Regulatory Activities
mRNA	messenger ribonucleic acid
NADP	nicotinamide adenine dinucleotide phosphate
NOAEL	no-observed-adverse-effect-level
PCR	polymerase chain reaction
PT	Pro thrombin Time
PTT	partial thromboplastin time
RBC	red blood cell
RNA	ribonucleic acid
SAE	serious adverse event
SD	standard deviation

14March2019

[figure not shown]
SMF	Site Master File
SOC	System Organ Class
SRC	Safety Review Committee
TIA	transient ischemic attack
U-VEGF121	Urinary Vascular Endothelial Growth Factors Isoform 121
Urinary VEGF-165	Urinary Vascular Endothelial Growth Factors Isoform 165
Urinary VEGF-189	Urinary Vascular Endothelial Growth Factors Isoform 189
Urinary VEGF-206	Urinary Vascular Endothelial Growth Factors Isoform 189
Urinary MCP-1	Monocyte chemoattractant protein 1,
Urinary Synaptopodin	Urinary Synaptopodin
Urinary TGF-beta	Urinary Transforming Growth Factor Beta
Urinary Podocalyxin	Urinary Podocalyxin
Urinary Nephryn	Urinary Nephryn
WBC	white blood cell
WHO	World Health Organization

Study Title	A Multicenter, Comparative Safety and Efficacy Study of ACTHar gel alone or in combination with oral Tacrolimus to reduce urinary proteinuria in patients with idiopathic DNA-JB9 Positive Fibrillary Glomerulopathy
Study Number	NN-002
Clinical Phase	Phase 4

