
Exclusion Criteria
	
5) Note: IF UP/Cr less than 2000 mg/gm, a formal 24-hour urine collection for total protein can be performed. The total 24-hour protein will need to >= 2000mg.
 
6) Blood pressure targeted to \leq 140/90 at the time of randomization
 
7) Patients with MGUS without history of myeloma WILL be eligible.
 
8) Patients with monoclonal staining for fibrillary fibers will be excluded
 
9) Patients with Type II non-insulin dependent diabetes WILL be eligible provided the renal biopsy does not show nodular Kimmelstiel Wilson lesions
 
Exclusion Criteria;
 
1) Patients with MGUS and history of myeloma WILL NOT be eligible
 
2) Patients with active viral production of either hepatitis B or C as evidence by historical PCR test positive for active viral shedding
 
3) HIV seropositivity
 
4) Renal biopsy data with > 50% Interstitial Fibrosis
 
5) Patient with active or a known history lymphoma
 
6) Patients with insulin Dependent diabetes mellitus will be excluded
 
Note: patients with Type II diabetes mellitus that are well controlled WITHOUT the need for insulin WILL be eligible for the study.
 
7) Patients with Type II non-insulin dependent diabetes WILL be eligible provided the renal biopsy does not show nodular Kimmelstiel Wilson lesions.
 
8) Patients receiving steroids, MMF, cyclophosphamide, Azathioprine or other immunosuppressive agent with 4 weeks of study randomization Note: Washout of these medications will be allowed at the screening visit
 
9) Patients having received Rituximab or B cell modifying biologic therapy within 6 months of randomization

----------------------------------	---

Primary Endpoint:	Primary Endpoint: The change in UP/Cr ratio in patients with biopsy proven Fibrillary GN after 12 months of treatment with treated with ACTHar gel (80 units SQ 2X/week) alone OR in combination with oral Tacrolimus (1.0 mg PO BID). The change in UP/Cr for each group will also be compared to baseline UP/Cr ratios prior to randomization

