
Number of total Clinic Visits
 
FACT-Trial: Study Design
	
conference call with the prospective patient will be arranged to discuss in details of the study; the risks/benefits of the study drug, as well as details regarding patient requirements and travel to and from the study site. The patient will be given time to review the consent with their families and other physicians.
 
If is determined by the Medical Director and the FACT Site PI that the patient is a likely candidate for the study, a travel agent will contact patient and make arrangements for airfare and overnight accommodations to visit the FACT PI. Both the airfare and overnight accommodations will be provided by NephroNet. If a patient lives within approximately 4 hours of the FACT site, they will be reimbursed for mileage and hotel. There will be a total of 13 visits per patient per site.
 
Patients agreeing to participate in the FACT sign consent at their first screening visit.
 
Thirteen (13) visits for total study: Pre-screening visits- two (2) Study Drug Treatment visits- six (6) Post Study Drug Treatment visits- five (5)
 
Study Design: This study will be a multi-center, prospective, randomized, open-labeled intervention trial of 34 patients randomized to 52 weeks of ACTHar gel alone or ACTHar gel plus oral Tacrolimus.
 
Drug Dosing:
 
Group-1: ACTHar gel alone-patients will be receive 80 units SQ Q 2X/week for 52 weeks
 
Group-2: ACTH gel 80 units 2X per week plus oral Tacrolimus (1.0 mg BID) titrating to a trough level of 4-6 ng/ml for 52 weeks
 
Note: Patient with type II diabetes will be allowed to dose at 24 units/day (0.3 mls SQ Q day) to reduce glucose fluctuations and simplify management of diabetes at the discretion of the PI.
 
Protocol-Schedule and Follow Up: Clinic Visits:

---	--

- **Visit 1: Pre-Randomization Screening & Consenting Visit:** Patients that have gone through the Pre-screening review and considered to be eligible for study participation will be seen by the local site PI for formal consenting two months prior to study randomization. The patient will then be seen by the FACT trial site PI who will perform a complete physical exam and obtain routine laboratory testing including a urine to protein Cr ratio.

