2) Percentage of patients in the ACTHar gel alone group that demonstrated additional reduction in UP/Cr

ratio following the addition of Tacrolimus at Week 52.

Hyperkalemia: Patient developing hyperkalemia defined as > 5.5 meq/L will undergo the following interventions:

Intervention #1: Review dietary sources of potassium and assess patient compliance with prescribed dietary restrictions.

Intervention #2: Adding or increasing dose of a loop diuretic. If they patient was already taking a diuretic as part of their standard of care regimen, the dose or frequency will be increased according to the discretion of the Site PI.

Intervention #3: For patients with continued hyperkalemia following intervention 1 & 2, the Site PI can consider adding a Thiazide diuretic (HCTZ or Metolazone) to the current loop diuretic.

Intervention #4: For patients with continued hyperkalemia following intervention 1 & 2 & 3, the dose of Tacrolimus can be reduced to 0.5 mg BID.

Combining Thiazide and Loop diuretic therapy to AM-PM doses

Intervention #5: For patients with continued hyperkalemia following intervention 1 & 2, 3, & 4, the patient can discontinued from Tacrolimus.

Note: Any Site PI that chooses to treat a study patient's hyperkalemia with Patiromer may do and keep the patient in the study. Any decision to use Patiromer is solely at the discretion of the Site PI.

Hyperglycemia: Patients developing intractable hyperglycemia defined as > 400 mg/dl can have their current diabetic medications modified. For patients with continued hyperglycemia despite increases in diabetic therapy, the dose of ACTHar gel can be reduced by 50%. Patients with persistent hyperglycemia can be withdrawn from the study at the discretion of the Site PI.

Note: Any Site PI choosing to use of Insulin to treat a study patient's hyperglycemia can do and keep the patient in the

study. Any decision to use institute Insulin therapy is solely at the discretion of the Site PI.

Lower Extremity Edema: Patients developing increasing lower extremity edema can have their diuretic regimen increased by either dose or frequency. Patients continuing to have edema with maximal Loop diuretics can be treated with dual Loop and Thiazide diuretic therapy. All decisions as the management of lower extremity edema will be left to the discretion of the Site PI.

Statistical Analysis Sample Size and Power.

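### HgbA1c is scheduled on treatment and in follow-up but never before treatment, so no change from baseline in HgbA1c can be calculated for the diabetic patients

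*Protocol*

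**What the plan says.** The Exclusion Criteria state in a note that "patients with Type II diabetes mellitus that are well controlled WITHOUT the need for insulin WILL be eligible for the study". Under Drug Dosing, patients with type II diabetes may use an alternative ACTHar regimen, "to reduce glucose fluctuations and simplify management of diabetes at the discretion of the PI". The Hyperglycemia section provides that "Patients developing intractable hyperglycemia defined as > 400 mg/dl can have their current diabetic medications modified", and goes on to allow ACTHar dose reduction, insulin and withdrawal. The protocol thus expects diabetic patients in the trial and expects glucose to be a concern in them.

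The schedule of assessments has a row for HgbA1c under Laboratory Assessments. It is marked in the columns for Visits 5 to 7, Visit 8, Visits 10 to 12 and Visit 13, and is blank at Visits 1, 2 and 3. Footnote 2 to that row reads "HgbA1c will be optional for diabetic patients left to discretion of the site PI". The text for Visits 1 to 3 refers only to routine laboratory work and does not name HgbA1c.

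The Study Design paragraph describes "34 patients randomized to 52 weeks of ACTHar gel alone or ACTHar gel plus oral Tacrolimus", so ACTHar gel is given in both arms.

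**The concern.** The protocol collects HgbA1c up to eight times per diabetic patient and has no scheduled value to compare any of them with. A raised value at month 3 or month 12 could reflect the study treatment or the patient's control on entry, and the scheduled HgbA1c data could not separate the two. Eligibility depends on diabetes being well controlled, yet no HgbA1c is scheduled at entry to document it.

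Because testing is at the investigator's discretion, the values that do arrive may come from a selected set of patients and visits. At stake is how the glycemic safety data can be read in a subgroup where the protocol itself foresees glucose problems. A statistical analysis plan cannot repair this, because it cannot recover a sample that was never scheduled.

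**Working it through.** The protocol gives no figure to reproduce here. The check is a reading of the schedule by column, followed by a question about what comparison the design leaves.

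**1. Is the blank real, or a product of text extraction?** The rows were matched to the ten visit columns, with neighbouring rows as an alignment check.

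| Row | V1 | V2 | V3 | V4 | V5–7 | V8 | V9 | V10–12 | V13 |
|---|---|---|---|---|---|---|---|---|---|
| CBC | X | X | X | | X | X | | X | X |
| CMP | X | X | X | | X | X | | X | X |
| UP/Cr | X | X | X | | X | X | | X | X |
| HgbA1c | | | | | X | X | | X | X |
| Tacrolimus trough | | | | | X | X | | | |

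The rows line up, and the UA row has the same marks as CBC and CMP. HgbA1c shares every later mark with these panels and lacks only the three marks up to randomization. The blank is in the schedule itself.

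**2. Count of scheduled time points.**
- Before treatment (V1, V2, V3): HgbA1c 0, CMP 3.
- On treatment (months 3, 6, 9, 12): HgbA1c 4.
- Follow-up after treatment (months 15, 18, 21, 24): HgbA1c 4.
- Total HgbA1c: 0 + 4 + 4 = 8, all optional under footnote 2.

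**3. What change can be computed?** Change from baseline at month t is HgbA1c(t) − HgbA1c(baseline). The second term is not scheduled for anyone, so the difference is undefined from scheduled data at all eight time points. What remains, where sites choose to test, is month 3 to month 12 (within treatment) and month 12 to month 24 (on to off treatment). Neither uses a pre-treatment reference, since month 3 is already three months into therapy.

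**4. Can the randomized comparison replace the baseline?** Arm 1 receives ACTHar gel; arm 2 receives ACTHar gel plus tacrolimus. The difference between arms estimates what tacrolimus adds. The ACTHar component is common to both and cancels, so its effect on HgbA1c can be viewed only within patients against a pre-treatment value.

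**5. How many patients?** The protocol does not give the number with diabetes. Assuming 20% to 40% of 34: 0.20 × 34 = 6.8 and 0.40 × 34 = 13.6, or about 7 to 14 patients. This range is an assumption and is used only to size the cost.

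**The case against.** The strongest case on the other side accepts the reading of the schedule and disputes what follows from it. Most of it stands as a limit on the point.

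- **An objective that cannot be met.** A reader might infer that the trial has a glycemic objective it cannot answer, because the Secondary Endpoint section begins: "Fibrillary GN patients with concurrent Type II diabetes mellitus: To determine whether ACTHar gel therapy resulted in". The sentence breaks off in the text at hand. Its outcome might be glycemic, but could equally be proteinuria, eGFR or adverse events, so the point does not rest on it.
- **No glycemic change measurable at all.** This goes too far. The "comprehensive metabolic panel" is drawn at Visits 1, 2 and 3 and at later laboratory visits. Its components are not listed; if glucose is among them, change in glucose from baseline is available. That would still not be change in HgbA1c, the measure the schedule also includes.
- **Glycemic harm left uninterpretable.** The documents do not support this either. The hyperglycemia rule is defined by glucose, adverse events are collected from Visit 3 to Visit 13, and their frequencies are compared by Fisher's exact test. None of that needs a baseline HgbA1c.
- **Upward bias from optional testing.** A reader might assume that sites will test when glucose looks poor and so raise the observed mean. The protocol does not say when sites will test. Selective missingness is a risk; its direction is not established.
- **A baseline would settle attribution.** It would not. The change would remain an uncontrolled before–after difference, affected by the permitted changes in diabetic medication, insulin and ACTHar dose.
- **Existing records.** Records are reviewed before Visit 1 and part of the pre-screening text is missing from this copy, so some patients may have an earlier HgbA1c on file. The supportable statement is that no baseline is scheduled, not that no patient has one.

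None of these objections supplies a scheduled pre-treatment HgbA1c, and that gap is the point.

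**Conclusion.** The point holds in limited form. HgbA1c has 0 scheduled values before treatment, 4 on treatment and 4 in follow-up, all optional. Change in HgbA1c from baseline cannot be calculated from scheduled data for any diabetic patient, and the between-arm comparison is no substitute because both arms receive ACTHar gel. Discretionary testing adds a risk of selective missingness.

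The conclusion rests on the schedule columns as read above, whose alignment the neighbouring rows confirm, and on the HgbA1c row being meant for diabetic patients, as footnote 2 implies. It does not need the truncated aim or the assumed share of diabetic patients. It is a low-cost improvement to subgroup safety data and has no bearing on the primary endpoint or the sample size.

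**What to change.** In the schedule of assessments, mark HgbA1c at Visit 3. Amend footnote 2 so that, in diabetic patients, the test is required for data collection at Visits 3 and 8 and stays optional at the other marked visits. Both visits already have blood drawn for CBC and CMP, so no new visit or draw is needed. The sample at Visit 3 should be taken before the first dose, since a missed baseline cannot be obtained later.

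Report the change from Visit 3 to Visit 8 descriptively, labelled as an uncontrolled within-patient change, with the number tested out of the number of diabetic patients and any changes in diabetic medication shown alongside. The change concerns data collection only and attaches no treatment rule to the result.

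The cost is a schedule edit plus one assay per diabetic patient at Visit 3, and a second at Visit 8 where the site would not otherwise have tested. Under the assumed 7 to 14 diabetic patients, that is 7 to 14 assays at Visit 3 and at most 14 to 28 in all (2 × 7 to 2 × 14).
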